6.7. Other Evaluations

6.7.1. Bone and Renal Markers

The following biological specimens will be collected in this study. The specific analyses will include, but will not be limited to, the biomarkers listed below.

- Urine Biomarkers including, but not limited to, retinol binding protein (RBP) and beta-2 microglobulin (for all subjects except Part A, cohort 2 [ESRD subjects on HD])
- Serum Bone Biomarkers including, but not limited to, C-type collagen sequence (CTX) and procollagen type 1 N-terminal propeptide (P1NP)

These specimens will be collected in a fasted state at Baseline and Weeks 4, 12, 24, 48, 72, and 96/ED. Samples may be stored by Gilead Sciences for a period of up to 15 years at the end of the study.

CCI

6.7.2. Intensive Pharmacokinetic Substudy (Optional)

CCI

CCI [REDACTED]

[REDACTED]

[REDACTED]

6.8. Resistance Surveillance and Virologic Rebound Management

Sequence analysis of the HBV polymerase/reverse transcriptase (pol/RT) for potential resistance mutations may be attempted for any subject with HBV DNA ≥ 69 IU/mL at Baseline and for subjects who experience viremia (HBV DNA ≥ 69 IU/mL) at Weeks 24, 48, and 96/ED. Phenotypic analysis will be performed for subjects that are subjected to sequence analysis.

As it may not be known at the time of the visit whether a patient is viremic or if it will be their last study visit, a separate serum sample for potential resistance surveillance will be collected at each study visit.

In the event of unconfirmed virologic rebound (HBV DNA ≥ 20 IU/mL), subjects will be asked to return to the clinic for a scheduled or unscheduled blood draw. For virologic rebound occurring within the first 12 weeks of the study, the next scheduled visit will be used for follow up. For virologic rebound occurring after Week 12, the subject will return for an unscheduled visit within 2-3 weeks after the date of the original test that resulted with HBV DNA virologic rebound for confirmation of virologic rebound. At this follow up visit, a serum blood sample for resistance testing will be obtained. For unscheduled visits, the subject will be required to bring their supply of study drug with them and be assessed for adherence by pill count, and if necessary, the subject will be re-counseled on adherence to study medication.

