- 13) Use of investigational agents within 3 months of Screening, unless allowed by the Sponsor
- 14) Use of any prohibited medication as described in Section 5.3.

Part A Only (renal impairment):

- 1) Current or historical evidence of clinical hepatic decompensation (e.g., ascites, encephalopathy or variceal hemorrhage)
- 2) Abnormal hematological and biochemical parameters, including:
 - Hemoglobin < 9 g/dL
 - Absolute neutrophil count < 750/mm³
 - Platelets ≤ 50,000/mm³
 - AST > 10 × ULN
 - Albumin < 3.0 g/dL
 - Total bilirubin > 2.5 × ULN
 - INR > 1.5 × ULN (unless stable on anticoagulant regimen)
- 3) Subjects with ESRD (i.e. eGFR_{CG} < 15 mL/min) not on HD, or those on other forms of renal replacement therapy (i.e. peritoneal dialysis)

Part B Only (hepatic impairment):

- 1) Active variceal bleeding within 6 months or prior placement of a portosystemic shunt (such as transjugular intrahepatic portosystemic shunt [TIPS])
- 2) History of hepatorenal syndrome, hepatopulmonary syndrome, Grade 3 or Grade 4 hepatic encephalopathy, or spontaneous bacterial peritonitis within 6 months of Screening

- 3) Grade 2 hepatic encephalopathy at Screening
- 4) MELD score ≥ 30
- 5) Abnormal hematological and biochemical parameters, including
 - Absolute neutrophil count $< 750/\text{mm}^3$
 - Platelets $< 30,000/\text{mm}^3$
 - Hemoglobin $< 8.0 \text{ g/dL}$

Study Procedures/
Frequency:

- Screening Visit
- Treatment Period Visits: Baseline/Day 1, Weeks 4, 8, 12, 24, 36, 48, 60, 72, and 96/Early Discontinuation (ED)
- Subjects in Part A (renally impaired) who permanently discontinue study drug (either prematurely or after completing 96 weeks of treatment) for reasons other than HBsAg loss with confirmed seroconversion to anti-HBs will be followed every 4 weeks for 24 weeks off treatment or until initiation of appropriate, alternative HBV therapy, whichever occurs first. Use of appropriate, alternative HBV therapy is strongly encouraged.
- For subjects in Part B (hepatic impairment) who permanently discontinue study drug, immediate initiation of appropriate, alternative HBV therapy is strongly recommended.
- Review of concomitant medications, assessment for adverse events, and vital signs and weight measurement will be conducted at all study visits.

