- Laboratory analyses (serum chemistry and liver function tests, hematology, eGFR_{CG}, urinalysis [for all subjects except only where available for subjects in Part A, Cohort 2 (ESRD subjects on HD)], and plasma HBV DNA level) will be conducted at all study visits.

Screening visit assessments include:

- Complete physical examination with height, body weight, vital signs, and medical history (including HBV disease and treatment history)
- Pregnancy testing (for females of childbearing potential)
- Plasma HBV DNA level (must be $< 20 \text{ IU/mL}$ by central laboratory at time of Screening to be eligible)
- HBV serology (qualitative HBsAg and HBeAg; HBeAb and HBsAb reflex testing will be performed as needed) and quantitative HBsAg

- HCV, HDV and HIV testing
- Baseline DXA scans of the hip and spine can be performed at any time during the Screening period, but should be conducted at least 14 days prior to the first dose of study drug to ensure an acceptable pre-dose DXA scan.
- INR and alpha fetoprotein (AFP); an AFP > 50 ng/mL at Screening must have an appropriate evaluation (e.g., CT scan if not performed within the previous 6 months) in order to rule out HCC prior to being permitted to enter the study.
- CPT ([Appendix 7](#)) and MELD Scores for Part B subjects (hepatic impairment) only
- Urine drug screen (for all subjects except only where available for subjects in Part A, Cohort 2 [ESRD subjects on HD])
- ECG

Baseline and On Treatment assessments include:

- Complete physical examinations with body weight and vital signs will be performed at Baseline, Weeks 24, 48, 72, and 96/ED. A symptom driven physical exam will be performed at all other visits.
- Pregnancy testing (for females of childbearing potential)
- HBV serology (qualitative HBsAg and HBeAg) and quantitative HBsAg will be performed at Baseline and Weeks 12, 24, 36, 48, 60, 72, and 96/ED. HBeAb and HBsAb reflex testing will be performed as needed.
- Fasting blood sample for metabolic assessment (glucose and lipid panel [total cholesterol, HDL, direct LDL, and triglycerides]) at Baseline and Weeks 24, 48, 72, and 96/ ED
- Fibrotest[®] at Baseline and at Weeks 24, 48, and 96/ED
- CPT ([Appendix 7](#)) and MELD Scores at Baseline and at Weeks 24, 48, and 96/ED for Part B subjects (hepatic impairment) only
- Fracture Risk Assessment (Baseline only)
- Vitamin D assessment at Baseline and at Weeks 24 and 48

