6.5. Early Discontinuation (ED)/Unscheduled Visit

A subject should attend an unscheduled visit if requested by the sponsor or the investigator.

The assessments at the unscheduled visits are at the investigator's discretion. At all unscheduled visits initiated for the purpose of confirming virologic rebound a serum blood sample for resistance testing must be collected.

If a subject discontinues study dosing (for example, as a result of an AE), every attempt should be made to keep the subject in the study and continue to perform the required study-related follow-up and procedures (see Section 6.6, Criteria for Discontinuation of Study Treatment). If this is not possible or acceptable to the subject or investigator, the subject may be withdrawn from the study.

The ED Visit should be performed within 72 hours (i.e., visit window is + 3 days) of the last study drug dose.

- Complete physical exam with vital signs (blood pressure, pulse, respiration rate and temperature) and body weight
- ECG (subjects must rest quietly in the supine position for a minimum of 5 minutes prior to the recording)
- DXA scan of spine and hip to be performed within \pm 14 days of the expected visit date and is done only if not done within the past 12 weeks of the ED visit
- Review concomitant medications
- Review adverse events
- Fasting blood sample for serum bone biomarkers and metabolic assessment (glucose and lipid panel [total cholesterol, HDL, direct LDL, and triglycerides]) – no food or drinks, except water, at least 8 hours prior to blood collection (only collected if not done in the last 12 weeks)
- Fasting urine sample for renal biomarkers for all subjects except for Part A, Cohort 2 (ESRD subjects on HD) – no food or drinks, except water, at least 8 hours prior to blood collection(only collected if not done in the last 12 weeks)

- Blood sample for serum chemistry and liver function tests (including PT/INR), hematology, plasma HBV DNA level, serum HBsAg (quantitative), HBV serology (qualitative HBsAg and HBeAg), eGFR_{CG}, virology (resistance surveillance), sparse plasma PK (all subjects except Part A, Cohort 2 [ESRD subjects on HD]), and serum and plasma for storage
- Blood sample for Fibrotest[®]
- CPT ([Appendix 7] Assessment requires: total bilirubin, albumin, PT/INR, Ascites assessment, and Hepatic encephalopathy assessment) for Part B subjects (hepatic impairment) only

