- i Subjects must rest quietly in the supine position for a minimum of 5 minutes prior to the recording.
- j CPT [Appendix 7] assessment requires: total bilirubin, albumin, PT/INR, Ascites assessment, and Hepatic encephalopathy assessment. MELD assessment requires total bilirubin, serum creatinine, PT/INR, and serum sodium.
- k The visit window for the Week 24, Week 48, and Week 96 visits is –7 days only.
- l The Early Discontinuation (ED) visit should be performed within 72 hours of the last study drug dose (+ 3 days)

- m Subjects in Part A (renally impaired) who discontinue study drug due to HBsAg loss with confirmed seroconversion to anti-HBs on or after the Week 24 visit, will be followed off treatment every 4 weeks for 12 weeks and then per the original study visit schedule through Week 96/ED. Subjects in Part A (renally impaired) who have received at least one dose of study drug and permanently discontinue study drug for reasons other than HBsAg loss with confirmed seroconversion to anti-HBs will be followed every 4 weeks for 24 weeks off treatment or up to initiation of appropriate, alternative HBV therapy, whichever occurs first. Use of appropriate, alternative HBV therapy is strongly encouraged. For subjects in Part B (hepatic impairment) who permanently discontinue study drug, immediate initiation of appropriate, alternative HBV therapy is strongly recommended.
- n Any subject with a post baseline $eGFR_{CG} < 15$ mL/min must have serum creatinine measured again within 3 calendar days of receipt of results. At the time of this repeat serum creatinine assessment, serum Cystatin C will also be measured and the eGFR by CKD-EPI (cystatin C) will be calculated and compared with the baseline measurement. Any subjects who have an $eGFR_{CG} < 15$ mL/min that also experience $> 20\%$ reduction in eGFR by CKD-EPI (cystatin C) from baseline or who have other clinical and/or laboratory evidence of acute renal failure will be discussed with the Medical Monitor and may discontinue from study drugs.
- o Blood for selected bone biomarkers and urine for selected renal biomarkers will be collected in a fasted state. The fasting urine sample will be collected for all subjects except Part A, Cohort 2 (ESRD subjects on HD). Required for ED visit if the last sample was not collected within the last 12 weeks.

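### A virologic rebound first seen at the Week 12 visit is by default not rechecked until Week 24, about 84 days later; moving Week 12 into the existing 2-3 week recheck rule is a cheap improvement

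*Protocol*

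**What the plan says.** HBV DNA is measured at every visit: the Synopsis lists it among the laboratory analyses ("and plasma HBV DNA level) will be conducted at all study visits"). The schedule, also in the Synopsis, is "Treatment Period Visits: Baseline/Day 1, Weeks 4, 8, 12, 24, 36, 48, 60, 72, and 96/Early Discontinuation (ED").

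Section 6.8 defines unconfirmed rebound as HBV DNA ≥ 20 IU/mL and gives two follow-up rules:

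- Early: "For virologic rebound occurring within the first 12 weeks of the study, the next scheduled visit will be used for follow up".
- Late: "For virologic rebound occurring after Week 12, the subject will return for an unscheduled visit within 2-3 weeks" of the original test. A serum sample for resistance testing is taken at that follow-up visit.

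The Synopsis and footnote p of Appendix 2 repeat both rules. No separate rule covers the Week 12 visit.

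The adherence check is attached to unscheduled visits, at which "the subject will be required to bring their supply of study drug with them and be assessed for adherence by pill count", with re-counselling if needed. Section 6.5 leaves room for discretion: "A subject should attend an unscheduled visit if requested by the sponsor or the investigator".

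**The concern.** The two rules appear designed around visit spacing. Where visits are four weeks apart, the next one serves as the recheck; where they are far apart, an extra visit is called. The Week 12 visit falls on the wrong side of that split. The 12-week gap that follows it is as long as the gap after Week 24, yet a Week 24 rebound is rechecked in 2-3 weeks and a Week 12 rebound is left to the next scheduled visit. The protocol gives no reason for the difference.

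Section 1.4 names loss of virologic control as a risk of switching and offers frequent viral-load monitoring as mitigation. Under the default, a known rebound soon after the switch can go unconfirmed for about 12 weeks. Part B enrols subjects with CPT scores up to 12. Section 1.2.4.3 says TAF has not been evaluated in decompensated cirrhosis, and Section 1.3 says active HBV replication in decompensated disease raises the risk of progression and death.

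Drug accountability at the Week 12 visit does not replace the rebound-triggered adherence check, because the result may not be in hand then. Section 6.8 says so when explaining its sampling: "As it may not be known at the time of the visit whether a patient is viremic".

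**Working it through.** The plan states no figure for this interval, so there is none to reproduce. The check is calendar arithmetic on the schedule and windows.

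**Inputs** (days from Baseline, Week w = 7 × w)

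- Week 4: day 28, window ±3, so 25-31 (Section 6.3.1).
- Week 8: day 56, window ±3, so 53-59 (Section 6.3.2).
- Week 12: day 84, window ±3, so 81-87 (Section 6.3.3).
- Week 24: day 168, window −7 only, so 161-168 (Section 6.3.4; footnote k of Appendix 2, which begins "The visit window for the Week 24, Week 48, and Week 96 visits is", confirms it).
- Late branch: 2-3 weeks, so 14-21 days after the original test (Section 6.8).

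**Formulas.** Nominal gap = next nominal day − current nominal day. Shortest gap = earliest next day − latest current day. Longest gap = latest next day − earliest current day.

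| Rebound first seen at | Default recheck | Nominal days | Shortest | Longest |
|---|---|---|---|---|
| Week 4 | Week 8 | 56 − 28 = 28 | 53 − 31 = 22 | 59 − 25 = 34 |
| Week 8 | Week 12 | 84 − 56 = 28 | 81 − 59 = 22 | 87 − 53 = 34 |
| Week 12 | Week 24 | 168 − 84 = **84** | 161 − 87 = **74** | 168 − 81 = **87** |
| After Week 12 | Unscheduled visit | 14-21 | 14 | 21 |

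**Ratios on nominal dates.** Against Weeks 4 and 8: 84 / 28 = 3.0. Against later rebounds: 84 / 21 = 4.0 to 84 / 14 = 6.0.

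**Comparison with Week 24.** The nominal gap from Week 24 to Week 36 is 252 − 168 = 84 days, the same as from Week 12 to Week 24. The long gap is therefore not special to Week 12; the missing early recheck is.

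**After the change.** The recheck would fall on day 84 + 14 = 98 to 84 + 21 = 105, that is Week 14 to 15. The gain is 84 − 21 = 63 to 84 − 14 = 70 days nominally, and 74 − 21 = 53 to 87 − 14 = 73 days across the windows.

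**Extra visits.** The documents give no rebound rate. Assuming 1% to 5% of the roughly 120 planned subjects have HBV DNA ≥ 20 IU/mL at Week 12: 0.01 × 120 = 1.2 to 0.05 × 120 = 6.

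**The case against.** The strongest reply is that the gap is narrow and already partly covered.

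- **Discretion.** Section 6.5 allows an unscheduled visit at any time and requires a resistance sample at any such visit made to confirm rebound. This stands, but the visit is optional for a Week 12 rebound and mandated for a later one.
- **Resistance sampling.** A virology sample is already drawn at Week 12, and planned on-treatment sequencing is for HBV DNA ≥ 69 IU/mL at Weeks 24, 48 and 96/ED. This stands: the Week 12 sample is not lost, and the resistance part of the gain is small. The larger gains are earlier confirmation and the adherence check.
- **No mandated action.** The protocol attaches no treatment change to a confirmed rebound; Section 6.6 lists therapeutic failure only as a reason that study drug may be stopped. True, but the same holds for later rebounds, for which a prompt recheck was still judged worthwhile.
- **ALT flares.** Section 7.5.5 triggers reflex HBV DNA testing, but only after a confirmed ALT above 2 × baseline and 10 × ULN, and it needs a blood draw of its own. It does not close the Week 12 to Week 24 gap.
- **Wording.** A Week 12 visit held on days 85-87 could literally be read as after Week 12 and sent to the late branch. This stands: for those visits the long wait depends on the reading. The ambiguity is a further reason to reword.
- **Effect on Week 24.** Checking adherence in Week 14 to 15 could change the Week 24 response of the few subjects concerned. This also stands and should be acknowledged, though the endpoint definition and the missing = failure rule do not change.

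**Conclusion.** The point holds as a design improvement. The default recheck of a Week 12 rebound is nominally 84 days away, against 28 days after Weeks 4 and 8 and 14-21 days after later visits, and no section requires anything sooner. This rests on the natural reading that the Week 12 visit belongs to the early branch. The consequence is delayed patient management, probably for only a few subjects. The documents do not show how often it would arise or that harm would follow from waiting. It is not an internal contradiction and does not alter the primary analysis. The change is nonetheless worth making, because the remedy is already in the protocol.

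**What to change.** In Section 6.8, the Synopsis and footnote p of Appendix 2, define the branches by visit. A rebound at a visit before the Week 12 visit is followed up at the next scheduled visit. A rebound at the Week 12 visit or later is followed up at an unscheduled visit 2-3 weeks after the date of the original test. Week 12 rebounds then receive the existing recheck, resistance sample and pill count, and a late Week 12 visit is no longer open to two readings.

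The cost is three matching wording edits, plus one unscheduled visit and blood draw for each subject with HBV DNA ≥ 20 IU/mL at Week 12. No new procedure is needed.

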7. ADVERSE EVENTS AND TOXICITY MANAGEMENT

7.1. Definitions of Adverse Events, Adverse Reactions, and Serious Adverse Events

7.1.1. Adverse Events

An adverse event (AE) is any untoward medical occurrence in a clinical study subject administered a medicinal product, which does not necessarily have a causal relationship with the treatment. An AE can therefore be any unfavorable and/or unintended sign, symptom, or disease temporally associated with the use of a medicinal product, whether or not considered related to the medicinal product. AEs may also include pre- or post-treatment complications that occur as a result of protocol specified procedures, lack of efficacy, overdose, drug abuse/misuse reports, or occupational exposure. Preexisting events that increase in severity or change in nature during or as a consequence of participation in the clinical study will also be considered AEs.

An AE does not include the following:

- Medical or surgical procedures such as surgery, endoscopy, tooth extraction, and transfusion. The condition that led to the procedure may be an adverse event and must be reported.
- Pre-existing diseases, conditions, or laboratory abnormalities present or detected before the screening visit that do not worsen
- Situations where an untoward medical occurrence has not occurred (e.g., hospitalization for elective surgery, social and/or convenience admissions)
- Overdose without clinical sequelae (see Section 7.6.1)
- Any medical condition or clinically significant laboratory abnormality with an onset date before the consent form is signed and not related to a protocol-associated procedure is not an AE. It is considered to be pre-existing and should be documented on the medical history CRF.

7.1.2. Serious Adverse Events

A **serious adverse event** (SAE) is defined as an event that, at any dose, results in the following:

- Death
- Life-threatening (Note: The term “life-threatening” in the definition of “serious” refers to an event in which the subject was at risk of death at the time of the event; it does not refer to an event that hypothetically might have caused death if it were more severe.)
- In-patient hospitalization or prolongation of existing hospitalization

- Persistent or significant disability/incapacity
- A congenital anomaly/birth defect
- A medically important event or reaction: such events may not be immediately life-threatening or result in death or hospitalization but may jeopardize the subject or may require intervention to prevent one of the other outcomes constituting SAEs. Medical and scientific judgment must be exercised to determine whether such an event is a reportable under expedited reporting rules. Examples of medically important events include intensive treatment in an emergency room or at home for allergic bronchospasm; blood dyscrasias or convulsions that do not result in hospitalization; and development of drug dependency or drug abuse. For the avoidance of doubt, infections resulting from contaminated medicinal product will be considered a medically important event and subject to expedited reporting requirements.

7.1.3. Clinical Laboratory Abnormalities and Other Abnormal Assessments as Adverse Events or Serious Adverse Events

Laboratory abnormalities without clinical significance are not recorded as AEs or SAEs. However, laboratory abnormalities (eg, clinical chemistry, hematology, and urinalysis) that require medical or surgical intervention or lead to IMP interruption, modification, or discontinuation must be recorded as an AE, as well as an SAE, if applicable. In addition, laboratory or other abnormal assessments (eg, electrocardiogram, x-rays, vital signs) that are associated with signs and/or symptoms must be recorded as an AE or SAE if they meet the definition of an AE or SAE as described in Sections 7.1.1 and 7.1.2. If the laboratory abnormality is part of a syndrome, record the syndrome or diagnosis (eg, anemia), not the laboratory result (ie, decreased hemoglobin).

For specific information on handling of clinical laboratory abnormalities in this study, please refer to Section 7.5.

7.2. Assessment of Adverse Events and Serious Adverse Events

The investigator or qualified subinvestigator is responsible for assessing AEs and SAEs for causality and severity, and for final review and confirmation of accuracy of event information and assessments.

7.2.1. Assessment of Causality for Study Drugs and Procedures

The investigator or qualified subinvestigator is responsible for assessing the relationship to IMP therapy using clinical judgment and the following considerations:

- **No:** Evidence exists that the adverse event has an etiology other than the IMP. For SAEs, an alternative causality must be provided (eg, pre-existing condition, underlying disease, intercurrent illness, or concomitant medication).
- **Yes:** There is reasonable possibility that the event may have been caused by the investigational medicinal product.

It should be emphasized that ineffective treatment should not be considered as causally related in the context of adverse event reporting.

The relationship to study procedures (eg, invasive procedures such as venipuncture or biopsy) should be assessed using the following considerations:

- **No:** Evidence exists that the adverse event has an etiology other than the study procedure.
- **Yes:** The adverse event occurred as a result of protocol procedures, (e.g., venipuncture)

